6.2 By Visit

Informed consent

Informed consent must have been given voluntarily by each subject before the study specific procedures are initiated. A medical history will be performed.

Clinical status

Weight, height, blood pressure, pulse, ECG, ETCO₂ and SpO₂ will be performed before each session

Concomitant medication

All concomitant medication (incl. vitamins, herbal preparation and other "over-the-counter" drugs) used by the subject within 28 days of treatment start will be recorded in the CRF.

6.2.1 Before Treatment Starts

- Evaluating patient eligibility: The subjects should be in good health and not have any chronic illness. Both sex will be included. The subject will be recruited from the general population.
- Assessing baseline values of parameters used as end-points: Each session starts with a CPT (time -15 minutes), see flow-chart 6.1. The NRS values from the first CPT are the baseline values the end-points will be evaluated from in each session.

6.2.2 During Treatment

Each session starts with a CPT (time -15 minutes). Then a 10 minutes rest before the subject receives a syringe of either NaCl or a dose of fentanyl intravenously (time -5 min). At the same time the subject begins to inhale either metoxyflurane or NaCl through the inhalator. The subject should first take 10 breaths through the inhalator. This will take approximately 1-1.5 minutes. The subject then takes a break, and then inhales the rest of the dosage before time zero.

At time zero a new CPT will be performed. At time 15 min the last CPT will be performed.

The subjects will undergo CPT (cold pressor test) to determine the analgesic effect of the drugs. (13,14) The CPT will be conducted using a temperature-controlled bath with circulating 3°C water (FP 45-HE Refrigerated/Heating Circulator, Julabo Labortechnik, 77960 Seelback, Germany). The subjects submerge their right hand to the wrist with fingers abducted for up to 90 s. The endpoints are NRS scores every 10 s. This test will be performed 3 times for each session.

6.2.3 End of Treatment and/or End of Study Visit

The actual implementation of the study will take 30 minutes. We estimate 30 minutes of preparation and 1 hour of observation after the execution of the protocol. Totally, each session will last for 2 hours.

6.2.4 Withdrawal Visit

If one participant experience very unpleasant or a severe adverse effect during a session, the session will be terminated. The participant will then be excluded from the rest of the study.

6.2.5 After End of Treatment (Follow-up)

After ending the last of 4 sessions, there will be no further follow-up

6.3 Criteria for Patient Discontinuation

Subjects may be discontinued from study treatment and assessments at any time. Specific reasons for discontinuing a subject for this study are:

- Voluntary discontinuation by the patient who is at any time free to discontinue his/her participation in the study, without prejudice to further treatment.
- Safety reason as judged by the Principal Investigator
- Major protocol deviation
- Incorrect enrolment i.e., the patient does not meet the required inclusion/exclusion criteria for the study
- Patient lost to follow-up
- A female patient becoming pregnant
- Deterioration in the patient's condition which in the opinion of the Principal Investigator warrants study medication discontinuation (to be records as an AE or under Investigator Discretion)
- Patient's non-compliance to study treatment and/or procedures
- Serious adverse effects of any of the drugs

6.4 Procedures for Discontinuation

6.4.1 Patient Discontinuation

Subject who gets any kind of severe adverse effects will be followed up.

All patients randomized will be included in the study population.

Patients who withdraw or are withdrawn from the study after randomisation cannot be replaced.

6.4.2 Trial Discontinuation

The whole trial may be discontinued at the discretion of the PI or the sponsor in the event of any of the following:

- Occurrence of AEs unknown to date in respect of their nature, severity and duration
- Medical or ethical reasons affecting the continued performance of the trial
- Difficulties in the recruitment of patients
- Cancellation of drug development

The sponsor and principal investigator(s) will inform all investigators, the relevant Competent Authorities and Ethics Committees of the termination of the trial along with the reasons for such action. If the study is terminated early on grounds of safety, the Competent Authorities and Ethics Committees will be informed within 15 days.

6.5 Laboratory Tests

No laboratory tests will be performed.

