4.3 Inclusion Criteria

1. Healthy volunteers
2. Age 18 – 64
3. Both sex
4. No chronic disease
5. No regular medication
6. Recruited from the general population
7. Signed informed consent and expected cooperation of the subjects for the treatment and follow up must be obtained and documented according to ICH GCP, and national/local regulations

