4.4 Exclusion Criteria

1. Use of pain medication the last 2 days before a session
2. Use of complementary medicine the last 2 days before a session
3. Use of regular medication
4. Previous substance abuse
5. Pregnancy
6. Know allergies or serious side effects to opioids or metoxyflurane
7. Use of alcohol last 24 h before each session
8. **Exclusion criteria with respect to fentanyl:**
9. Hypersensitivity opposite the active substance (fentanyl) or other opioids
10. Hypersensitivity opposite the excipients (to fentanyl): sodiumchlorid, water for injection, hydrochloric acid or sodium hydroxide
11. Respiratory depression without artificial ventilation

12. Use of MAO-inhibitor or use of MAO-inhibitor by two weeks before inclusion

13. Elevated intracranial pressure or brain trauma

14. Hypovolemia or hypotension

15. Myasthenia gravis

16. Exclusion criteria with respect to metoxyflurane:

17. Use metoxyflurane as anesthetic

18. Hypersensitivity opposite metoxyflurane or fluorinated anesthetics

19. Hypersensitivity opposite the excipient (to metoxyflurane): Butylhydroksytoluen

20. Malignant hyperthermia or persons with suspect genetic predisposition for malignant hyperthermia

21. History (to the volunteer or family) of serious adverse effects after administration of inhalation anesthetics

22. Volunteers showing sign of liver damage after use of metoxyflurane or halogenated anesthetics

23. History of liver disease

24. Clinical significant reduced kidney function or history of kidney disease

25. Changed of level of consciousness of any cause, including brain trauma, drugs or alcohol

26. Clinical detected cardiovascular instability

27. Clinical detected respiratory depression

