5.6 Concomitant Medication

No use of pain medication and complementary medicine the last 2 days before a session. No concomitant drugs are allowed to take.

Prohibited medication:

- Hypersensitivity opposite the active substance (fentanyl) or other opioids.
- Hypersensitivity opposite metoxyflurane, fluorinated anesthetics or butylhydroksytoluen
- MAO-inhibitor or use of MAO-inhibitor by two weeks before inclusion.

If any adverse effects we have rescue medications: naloxone (adverse effects to opioids), adrenalin (low blood pressure, anaphylaxis), atropine (low pulse) and ephedrine (low blood pressure and/or low pulse)

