6 STUDY PROCEDURES

6.1 Flow Chart

Screening period within 1-14 days of treatment. Inclusion/exclusion evaluation. A medical history will be performed.

Three pilots will be performed before the study start to investigate whether the two selected doses are representative to compare with the 3 ml metoxyflurane dose. If the pilots demonstrate large differences in the CPT scores at time zero between the selected fentanyl doses and metoxyflurane, a change in the protocol has to be performed. This will lead to an application to REK about the changes (and the Norwegian Medicines Agency).

Flow chart:

Time (min)	-15	-10	-5	0	5	10	15
Control (C)	CPT		placebo (NaCl) i.v. placebo (NaCl) inhal; continuous	CPT			CPT
Fentanyl (F1)	CPT		F1 0.025 mg i.v. placebo (NaCl) inhal; continuous	CPT			CPT
Fentanyl (F2)	CPT		F2 0.05 mg i.v. placebo (NaCl) inhal; continuous	CPT			CPT
Metoxyflurane (M)	CPT		placebo (NaCl) i.v. M 3 ml inhal; continuous	CPT			CPT

Abbreviations: NaCl: natriumchloride, i.v: intravenously, inhal: inhalation, CPT: Cold pressor test.

Each session starts with a CPT (time -15 minutes). Then a 10 minutes rest before the subject receives a syringe of either NaCl or a dose of fentanyl intravenously (time -5 min). At the same time the subject begin to inhale either metoxyflurane or NaCl through the inhalator. The subject should first take 10 breath through the inhalator. This will take approximately 1-1.5 minutes. The subject then take a break, and then inhale the rest of the dosage before time zero.

At time zero a new CPT will be performed. At time 15 min the last CPT will be performed.

The subjects will undergo CPT (cold pressor test) to determine the analgesic effect of the drugs.(13,14) The CPT will be conducted using a temperature-controlled bath with circulating 3°C water (FP 45-HE Refrigerated/Heating Circulator,

Julabo Labortechnik, 77960 Seelback, Germany). The subjects submerge their right hand to the wrist with fingers abducted for up to 90 s. The endpoints are NRS scores every 10 s. This test will be performed 3 times for each session.

The actual implementation of the study will take 30 minutes. We estimate 30 minutes of preparation and 1 hour of observation after the execution of the protocol. Totally, each session will last for 2 hours.

A cannula will be placed on the subject left hand back. The right hand will be submerged into the ice water.

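### Pregnancy excludes and discontinues, but the protocol rules out laboratory tests and gives no means beyond history to establish pregnancy status at entry or across the four sessions

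*Combined protocol and SAP*

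**What the plan says.** **Who may enter.** Section 4.3 admits both sexes from 18 to 64 years. Pregnancy is exclusion no. 5 in section 4.4. Section 6.3 lists "A female patient becoming pregnant" among the reasons for discontinuing a subject.

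**How status is checked.** Section 6.1 describes screening as "Screening period within 1-14 days of treatment. Inclusion/exclusion evaluation. A medical history will be performed". Section 7.3 asks for a detailed history before inclusion, directed especially at the exclusions in 4.4. Section 6.2 lists the checks before each session: body measurements, blood pressure, pulse, ECG, end-tidal CO₂ and oxygen saturation. Section 6.5 reads, in full, "No laboratory tests will be performed".

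**Medication.** Section 4.3 no. 5 requires "No regular medication", section 4.4 no. 3 excludes "Use of regular medication", and section 5.6 adds "No concomitant drugs are allowed to take". None of the three mentions contraceptives.

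**The concern.** Two stated safety rules depend on a fact that the protocol gives the site almost no way to establish. History can reveal a pregnancy that the volunteer knows of or suspects. It cannot reveal one that she does not. Section 6.5 makes this more than an omitted detail, because the protocol states affirmatively that no laboratory testing is done.

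The discontinuation rule in 6.3 is the weaker of the two. It concerns pregnancy that begins after entry, yet no check of pregnancy status is specified after screening.

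At stake is the exposure of a healthy volunteer, who by section 7.3 can expect no particular benefit, to methoxyflurane and two fentanyl doses while she meets an exclusion. A missed case is also unlikely to surface later. Routine adverse event collection is required only until at least one hour after the last dose (8.3) and there is no follow-up (6.2.5), although birth defects are among the seriousness criteria in 8.1.2.

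**Working it through.** No figure in the plan bears on this point directly, so the check is mainly a comparison of passages, with short arithmetic on timing and cost.

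**1. Can each rule be applied as written?**

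| Rule | When it must be applied | Means specified |
|---|---|---|
| Exclusion no. 5 (4.4) | At screening | Medical history (6.1, 6.2, 7.3) |
| Discontinuation (6.3) | Throughout the four sessions | None specific to pregnancy; the 6.2 pre-session list does not include it |
| Any laboratory confirmation | – | Ruled out by 6.5 |

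A site that follows all of these sections exactly can dose a volunteer with an unrecognised pregnancy, at the first session or a later one, without departing from any procedure.

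**2. Exposure.** Sections 2.2 and 6.1 give four sessions per volunteer: control, fentanyl 0.025 mg, fentanyl 0.05 mg and methoxyflurane 3 ml. Active drug is given in 4 − 1 = 3 of them.

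**3. Timing.** Section 5.3 sets a gap of at least 3 days and no maximum.
- First to last session: at least 3 gaps × 3 days = 9 days.
- Screening is 1 to 14 days before treatment, so the last session falls at least 1 + 9 = 10 days after the screening history.
- No upper limit can be calculated, because no maximum gap is stated.

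**4. Number of tests under the fix.** Per woman: 1 at screening + 4 sessions = 5. The documents do not give the number of women. If six of the 12 volunteers are women of childbearing potential (an assumption), 6 × 5 = 30 tests. The range runs from 0 (none) to 12 × 5 = 60 (all).

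**5. Effect on power.** Section 10.1 states n = 10 for 80% power (paired t-test, difference 0.5, SD of differences 0.5, two-sided 0.05). With standardised difference 0.5/0.5 = 1.0, the exact noncentral-t calculation gives 80.3% at n = 10, which reproduces the plan, and 88.3% at the 12 enrolled. Section 6.4.1 allows no replacement, so one volunteer lost to a pregnancy leaves 11, with 84.8% power. The matter is one of eligibility and safety, not of power.

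**The case against.** The strongest reply is that the protocol does provide for pregnancy. It excludes it, requires a history aimed at the exclusions, and foresees pregnancy during the study. Exclusions 1, 2 and 7 are tied to individual sessions, so the volunteer has to be questioned again at each visit. The term laboratory tests is not defined, and a bedside urine dipstick may fall outside it. The consent pages were not available for this review and may contain wording on pregnancy or contraception.

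Much of this stands, and it limits the claim. It would be wrong to say that a site cannot detect any pregnancy, or that history is certainly taken only once. What remains is that an unrecognised pregnancy escapes questioning however often the question is put, that no pregnancy question is specified at the sessions, and that no test of any kind is named in the text supplied. Consent wording would not by itself amend 6.5.

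A reader might also infer more from the medication rules: that they bar women who take a daily contraceptive pill, and so admit the women most likely to be unknowingly pregnant. The documents do not support this.
- Contraceptives are never named, so the bar is only one literal reading of an undefined term. Section 6.2 has medication from the 28 days before treatment start recorded, which suggests that some use was foreseen.
- Even on the literal reading, women using non-drug methods, sterilised women and postmenopausal women up to 64 remain eligible, and no figure in the documents ranks their risk.
- There is no figure on contraceptive use, so the share of women who might be turned away cannot be estimated.

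**Conclusion.** The point holds as a gap in verification. Sections 4.4 and 6.3 set two pregnancy rules, 6.5 excludes laboratory testing, and the text supplied specifies nothing beyond history to apply them. An unrecognised pregnancy would not be found by any specified procedure before dosing or between sessions. The change should be made, although the trial's statistical validity does not depend on it.

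The gap concerns every woman of childbearing potential among the 12 volunteers, each with up to three active-drug sessions over 9 days or more. The documents give neither the number of such women nor a rate of unrecognised pregnancy, so no probability of an event is claimed. The conclusion assumes that the removed consent pages do not specify a test.

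The status of hormonal contraception under 4.3 no. 5, 4.4 no. 3 and 5.6 is a separate, lesser point. It is an ambiguity that staff may settle differently from one volunteer to the next, not a demonstrated bar.

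**What to change.** 1. Reconcile 6.5 with 4.4 and 6.3. Amend 6.5 so that it excepts a urine pregnancy test for women of childbearing potential, at screening and before each session, and define that group, since the protocol does not. Record the result with the pre-session checks already listed in 6.2.
2. Separately, have the sponsor reconcile 4.3 no. 5, 4.4 no. 3 and 5.6 so that they state whether hormonal contraception is covered. This review does not prescribe which way that rule should go.

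**Cost.** One protocol amendment, which under 11.3 needs approval by the competent authority and the ethics committee, plus the dipsticks counted above. No extra visits or staff are needed, because every test falls on an existing contact. The sample size, endpoints and analysis are unchanged.

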7 ASSESSMENTS

7.1 Assessment of Response

The following parameters of response will be recorded:

Pain scores (NRS):

The subjects will undergo CPT (cold pressor test) to determine the analgesic effect of the drugs.(13,14) The CPT will be conducted using a temperature-controlled bath with circulating 3°C water (FP 45-HE Refrigerated/Heating Circulator, Julabo Labortechnik, 77960 Seelback, Germany). The subjects submerge their right hand to the wrist with fingers abducted for up to 90 s. The endpoints are NRS scores every 10 s. This test will be performed 3 times for each session.

7.2 Safety and Tolerability Assessments

Safety will be monitored by the assessments described below as well as the collection of AEs at every session. Significant findings that are present prior to the signing of informed consent must be included in the relevant medical history/ current medical condition page of the CRF. For details on AE collection and reporting, refer to Section 8.

Pulsoxymetry, ETCO₂ and ECG will be continuously monitored during the study. Necessary acute medical equipment is available (Lærdalsbag, suction, intravenous liquid, naloxone. In addition anesthetic drugs: adrenalin, atropine and ephedrine).

Side effects will be recorded: sedation, dizziness, itching, nausea and vomiting. Respiration frequency and non-invasive blood pressure will be recorded every 5. min

7.3 Other Assessments

Summary of benefit-risk to the volunteers in this study:

There are no special benefits to the volunteers to participate in this study.

It is important to record a detailed anamnesis before inclusion. Especially with respect to exclusion criteria mention in chapter 4.4

It is a certain risk that the participant may experience a feeling of «high» or drugged when he/she gets fentanyl intravenously. Therefore, previously drug-addicted will not be included in the study. The dosages of fentanyl are small

and the participants will be exposed repetitive times to the ice water test (cold pressor test - CPT). The CPT is considerable painful and a possibly feeling of "high" will disappear when the pain increase.

The participant will be informed about the painful ice-water test. The CPT is harmless, but participants that experience the pain as unbearable the experiment will be stopped.

Metoxyflurane may be nephrotoxic in anesthetic doses. 6 ml metoxyflurane is equivalent with 1.5 g. Nephrotoxic dose has been estimated to be approximately 20-24 g. (8). There are no published studies on cases of kidney failure with dosages of 3-6 ml. In our study, the participants receive only 3 ml once. Persons with any kind of history of kidney disease will not be included.

Common side effects like sedation, nausea, vomiting, dizziness, itching and respiration depression (especially to fentanyl) will be continuously monitored during the study. If some of the side effects become too bothersome to the participant, the experiment will be stopped.

Necessary acute medical equipment is available (Lærdalsbag, suction, naloxone, adrenaline, atropine and ephedrine) will be kept nearby.

Vital sign assessment (blood pressure and respiration frequency) will be registered every 5. min during each session. Continuous ECG, heart rate, ETCO₂ and SpO₂ measurement will be registered throughout each session. This close monitoring will help us in detecting severe adverse effects like malignant hyperthermia (elevated ETCO₂), anaphylactoid or anaphylactic reactions. The participants have intravenous access, and the i.v. access can of course be used in a setting of anaphylactoid or anaphylactic reactions.

All adverse events and serious adverse events will be reported as defined in section 8.1.1 will be recorded in the patient's CRF.

8 SAFETY MONITORING AND REPORTING

The investigator is responsible for the detection and documentation of events meeting the criteria and definition of an adverse event (AE) or serious adverse event (SAE). Each patient will be instructed to contact the investigator immediately should they manifest any signs or symptoms they perceive as serious.

The methods for collection of safety data are described below.

8.1 Definitions

8.1.1 Adverse Event (AE)

An AE is any untoward medical occurrence in a patient administered a pharmaceutical product and which does not necessarily have a causal relationship with this treatment.

An adverse event (AE) can therefore be any unfavorable and unintended sign (including an abnormal laboratory finding), symptom, or disease temporally associated with the use of a medicinal (investigational) product, whether or not related to the medicinal (investigational) product.

The term AE is used to include both serious and non-serious AEs.

AE that do not need to be recorded (expected AE): for opioid (fentanyl): sedation, dizziness, itching, nausea and vomiting are frequent AE's. If the AE's are mild and/or acceptable for the subject, the subject will not be excluded from the study and the AE do not need to be recorded. Mild respiration depression (resp frequency > 8/min) will be accepted as AE that do not need to be recorded.

If an abnormal laboratory value/vital sign are associated with clinical signs and symptoms, the sign/symptom should be reported as an AE and the associated laboratory result/vital sign should be considered additional information that must be collected on the relevant CRF.

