1.3 Rationale for the Study and Purpose

Traumatized patients frequently experience pain prehospital due to the fear of adverse cardiovascular effects (e.g. hypotension) and respiration depression of opioid treatment, leading to insufficient analgesia.(1,2) Therefore, there is of interest to investigate other analgesics that do not have these adverse effects.

In Norway, methoxyflurane has been approved for the emergency relief of moderate to severe trauma pain in conscious adult patients. Methoxyflurane (Penthrox®) do not have these adverse effects (hypotension and respiration depression). It is easy to administrate via an inhalator, and is therefore suitable for use prehospital. This would possible help to treat pain better prehospital.

There exists no data of how effective methoxyflurane is as an analgesic compared to an opioid. The aim of this study is to determinate the equipotent doses of inhaled methoxyflurane vs. intravenous fentanyl.

Twelve healthy volunteers (18 – 64 years) will be enrolled in a randomized, double blind, placebo-controlled, crossover study using a standard experimental pain model: CPT- Cold pressor test (ice water). Our group has used this experimental pain model in earlier studies and a crossover study is suitable to compare different drugs.(13,14)

Possible side effects will be recorded for both metoxyflurane and fentanyl: sedation, dizziness, itching, nausea and vomiting. Respiration frequency and non-invasive blood pressure will be recorded every as possible low blood pressure or respiration depression can occur.

The aim of this study is to determinate equipotent doses of inhaled metoxyflurane vs. intravenous fentanyl. We have chosen to compare with fentanyl (the comparator) because it is a well-known drug in clinical practice for acute pain treatment. In addition, both drugs have a fast onset (minutes) and the analgesic effect last for approximately the same time interval (20-30 min). Therefore, they are comparable in a clinical setting.

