Pulsoxymetry, ETCO₂ and ECG will be continuously monitored during the study. Necessary acute medical equipment is available (Lærdalsbag, suction, intravenous liquid, naloxone. In addition anesthetic drugs: adrenalin, atropine and ephedrine).

Side effects will be recorded: sedation, dizziness, itching, nausea and vomiting. Respiration frequency and non-invasive blood pressure will be recorded every 5. min

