8.2 Expected Adverse Events

The following side-effects/adverse events: respiratory depression, sedation, nausea, vomiting, pruritus, dizziness and headache will be registered in the CRF.

Such AEs will be registered in the AE/SAE section of the CRF. Further adverse events listed in the SmPCs for the study drugs will also be registered as AE/SAE if they occur

- 1) Pentrox® 3 ml / ATC-nr. N02B G09/ Inhalation vapour, Mundipharma, Norwegian version section 4 "Bivirkninger".
- 2) Fentanyl® 2 ml, 0.05 mg/ml /ATC-nr. N01A H01/ intravenous use, Hameln, Norwegian version section 4 "Bivirkninger".

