8.5.4 Clinical Study Report

The adverse events and serious adverse events occurring during the study will be discussed in the safety evaluation part of the Clinical Study Report.

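### Section 8.1.1 waives recording of mild expected effects that 8.2 says will be registered, in fentanyl-only wording that blinded staff cannot apply; 8.1.3 and the code-break rules also need reconciling

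*Combined protocol and SAP*

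**What the plan says.** Section 8.1.1 contains two waivers. The first reads "AE that do not need to be recorded (expected AE): for opioid (fentanyl): sedation, dizziness, itching, nausea and vomiting are frequent AE's"; the next sentence excuses such events from recording if they are mild, acceptable to the subject, or both. The second reads "Mild respiration depression (resp frequency > 8/min) will be accepted as AE that do not need to be recorded" and names no drug.

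Section 8.2 lists "respiratory depression, sedation, nausea, vomiting, pruritus, dizziness and headache will be registered in the CRF" and names the place: "Such AEs will be registered in the AE/SAE section of the CRF". It sets no severity threshold and does not limit the rule to one drug.

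Three other sections also require recording. Section 1.3 says "Possible side effects will be recorded for both metoxyflurane and fentanyl: sedation, dizziness, itching, nausea and vomiting". Section 6.1 says "Side effects will be recorded: sedation, dizziness, itching, nausea and vomiting", and 7.2 repeats it. Sections 7.3 and 8.5.1, however, refer back to 8.1.1 for what goes into the CRF.

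Under 8.4 the investigator records adverse events, and under 10.2.3 the investigators are blinded to the study medication.

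Two further statements bear on the same events. Section 8.1.3 refers to well-known opioid side effects included in the protocol and says that any such event counts as an SAE. On code breaks, 10.2.3 permits unblinding only when the subject's safety is threatened and reserves the decision to the principal investigator. It then says that the investigator breaks the code when an SAE occurs. Section 8.6 calls for a code break after a medical incident that was not expected; it neither defines such an incident nor says who decides.

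**The concern.** The same mild event is optional under 8.1.1 and mandatory under 8.2. The symptom waiver also turns on the drug given, which the person completing the CRF is not supposed to know. Mild events may then be recorded in some sessions and left out in others. The direction of any resulting imbalance between treatments cannot be predicted.

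These records have a stated use: "The adverse events and serious adverse events occurring during the study will be discussed in the safety evaluation part of the Clinical Study Report". They also bear on why the trial is being done. After naming hypotension and respiratory depression as the feared effects of opioids, 1.3 continues: "Therefore, there is of interest to investigate other analgesics that do not have these adverse effects". Mild respiratory depression is one of the waived effects.

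Taken literally, 8.1.3 would turn ordinary nausea or dizziness into an SAE. That would bring 24-hour reporting under 8.5.1 and a code break under 10.2.3.

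**Working it through.** The plan gives no figure to reproduce here. The check is a comparison of texts, with simple counts for scale.

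**1. Effects covered by both rules**

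| Effect in 8.2 | Waived in 8.1.1? | Drug named in the waiver |
|---|---|---|
| Sedation | yes, if mild or acceptable | fentanyl |
| Dizziness | yes, if mild or acceptable | fentanyl |
| Pruritus (itching) | yes, if mild or acceptable | fentanyl |
| Nausea | yes, if mild or acceptable | fentanyl |
| Vomiting | yes, if mild or acceptable | fentanyl |
| Respiratory depression | yes, if rate > 8/min | none |
| Headache | no | – |

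Waived: 5 + 1 = 6 of 7. Not waived: 7 − 6 = 1 (headache). Because the condition is mild *or* acceptable, an event that is not mild but that the subject tolerates may, read literally, also go unrecorded.

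**2. Sessions**

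- Inputs: 12 subjects (4.2), each receiving 4 treatments (5.3), two of which are fentanyl doses (2.2 and 6.1).
- Maximum sessions: 12 × 4 = 48.
- Fentanyl sessions: 12 × 2 = 24. The other 48 − 24 = 24 are 12 methoxyflurane and 12 control.
- 48 is an upper bound, because withdrawn subjects are not replaced (6.4.1).
- The conflict arises only where a mild or acceptable listed event occurs. No event rate is given, so affected sessions range from 0 to 48.

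**3. Link to the rationale**

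Section 1.3 names two opioid effects of concern, hypotension and respiratory depression. One of the two falls under the waiver.

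**4. The SAE sentence**

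Section 8.1.2 defines an SAE by seriousness criteria and calls for medical judgment. Section 8.4 gives nausea lasting several hours as an example of a severe event that is not an SAE. The sentence in 8.1.3 applies no seriousness criterion. Taken literally, mild nausea in a fentanyl session would be exempt from recording (8.1.1), due for registration (8.2) and an SAE (8.1.3).

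**5. Code break**

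| Place | Trigger | Who acts |
|---|---|---|
| 10.2.3, first statement | subject's safety threatened | principal investigator only |
| 10.2.3, last sentence | SAE | the investigator |
| 8.6 | unexpected medical incident, undefined | not stated |

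That makes three trigger wordings and two descriptions of who acts, with none in 8.6.

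**The case against.** The strongest reply is that the rules can be read together. The waiver is permissive, so a site that records everything satisfies both 8.1.1 and 8.2. The words about fentanyl may only explain which effects are frequent; the sentence that grants the waiver names no drug, so staff could apply it by symptom in every session. The references to 8.1.1 in 7.3 and 8.5.1 suggest that 8.2 is subject to it. The symptoms are also to be recorded as study assessments under 1.3, 6.1 and 7.2. Respiratory rate and blood pressure are taken every 5 minutes, and SpO2 and ETCO2 are monitored continuously, so the physiological data exist whatever is entered as an AE. No comparative tolerability analysis is specified. The sentence in 8.1.3 is probably a drafting slip, and a true SAE will ordinarily meet the safety condition for unblinding.

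Much of this limits the consequences, and I accept it as such. It does not remove the conflict. Applying the waiver by symptom departs from its heading and still contradicts 8.2, which names the AE/SAE section of the CRF and states no exception. The references back to 8.1.1 make matters worse in practice, since they lead staff to the waiver while 8.2 leads them to full registration. Recording respiratory rate is not the same as registering an event, and it does nothing for the five symptoms. On 8.1.3, other sections argue against the literal reading, which is a reason to correct the sentence. The code-break point is the least of the three: under 6.2.4 and 6.3 a subject with an SAE would generally give no later NRS scores, so what remains is a clear trigger and a clear decision-maker.

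**Conclusion.** The concern holds. For mild events, 8.1.1 and 8.2 give different instructions on six of the seven listed effects. As worded, the symptom waiver depends on treatment knowledge that the blinded recorder does not have, and it fits only 24 of at most 48 sessions.

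The damage is confined to the completeness and comparability of the safety data. Actual loss is not demonstrated and cannot be quantified from the documents. The session counts assume that all 12 subjects complete all four sessions, and the figure of 24 rests on reading the heading of the waiver as limiting it to fentanyl. The NRS endpoints, the sample size and the efficacy analysis are untouched. The 8.1.3 sentence contradicts 8.1.2 and 8.4 as written, though this was probably not intended. The code-break wording is a lesser inconsistency. Overall this should be fixed, and confidence in the textual conflict is high.

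**What to change.** - **8.1.1:** remove the recording waiver, or otherwise align it with 8.2, so that one rule that does not depend on treatment applies in every session. If alignment is chosen over removal, 8.2 may need a matching edit.
- **8.1.3:** reword so that an expected event is an SAE only if it meets the criteria in 8.1.2.
- **10.2.3 and 8.6:** reconcile the statements on what triggers a code break and on who decides. Which rule applies is for the sponsor and the investigators to settle.

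The cost is wording in four sections (8.1.1, 8.1.3, 8.6 and 10.2.3). No new assessment is needed: the five symptoms are already to be recorded under 6.1 and 7.2, all seven effects under 8.2, and respiratory rate is already taken every 5 minutes.
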